**AMENDMENTS:**

1.	2.	3.	4.
----	----	----	----

## 1. Introduction

Cognitive impairment is common in people diagnosed with schizophrenia (Harvey et al., 2022). The deficits are global and impact on both neurocognition (attention, memory, planning) and social cognition (difficulties perceiving and processing emotions) (Pinkham et al., 2014; Vaskinn & Horan, 2020). Approaches to remediation of these deficits have included integrated programs with a combined approach to neuro cognition and social cognition and stand-alone programs focussing either on neuro cognition or social cognition (Fernandez-Sotos et al., 2019; Iozzino et al., 2021; Trapp, Heid, Roder, Wimmer, & Hajak, 2022). There is evidence from randomized controlled trials and meta-analysis for the benefit of Cognitive Remediation therapy (CR) on global cognition (Effect Size ES =0.45) with greater benefit if CR is combined with some form of rehabilitation (ES=0.59) (Dark, Harris, Gore-Jones, Newman, & Whiteford, 2018). The core components of CR appear to be intensity of practice (2-4 times a week); the combination of drill and practice of tasks with strategy training and a context that facilitates use of new skills learnt. However, response to therapy is variable and research still needs to clarify conclusively the relevance of participants' characteristics and therapy implementation methods in influencing potential benefits.

The evidence for the mechanisms by which CR is effective are yet to be clarified (Jha, Lin, & Savoia, 2016). A core component of CR is strategic learning principles ensuring tasks are scaffolded based on previous successful achievement and chances of successful task completion are optimized. There is therefore close reinforcement of learning. One proposed potential mechanism for effect of CR is reward learning which potentially is the pathway to improved cognition and the motivational negative symptoms (Jha et al., 2016). In schizophrenia there is impairment in reward anticipation (Grimm et al., 2014; Subramaniam et al., 2015) and representation (Gold, Waltz, Prentice, Morris, & Heerey, 2008) leading to poorer decision-making, motivational deficits and negative symptoms (Billeke & Aboitiz, 2013; Gold et al., 2008; Juckel et al., 2006; Park et al., 2015).

Reward Learning (RL) is a term used to identify the cognitive processes responsible to adapt behaviour following positive or negative feedback. RL is a basic adaptive function of every living organism and provides the possibility to adapt and change in response to internal and environmental demands. This process has been studied extensively in neuroscience and linked to the brain dopamine system. The dopamine hypothesis of schizophrenia is the single most influential theory in our understanding of the neurochemical basis of the illness. This theory suggests that fundamental dysregulation in this system is responsible for the illness symptoms. Dysregulation in the dopamine system is also linked to RL abnormalities which in turn are thought to influence cognitive and

negative symptoms. A growing body of basic neuroscience literature has identified two complementary and interactive neural systems in the dopamine system responsible for predicting outcome and learning from feedback (Schultz, Dayan, & Montague, 1997). The first of these systems, responsible of rapid learning, is mediated by the basal ganglia. This system, referred to as the “fast system”, is believed to represent the predicted value of actions and rewards. These predictions bias actions and underlie learning based upon positive and negative feedback. The second slower system is based primarily in the prefrontal cortex, and allows more detailed, conscious and abstract representations of values and rewards. These representations of value are instrumental in allowing individuals to flexibly respond to reward value and adapt to novelty in the environment. There is consistent evidence that people with schizophrenia are impaired at making rapid behavioural adjustments in response to feedback and that these impairments are associated with negative and cognitive symptoms (Hanssen et al., 2020; Waltz & Gold, 2007; Waltz et al., 2010). Problems using this system are evident in situations requiring rapid change in responses to environmental changes when a situation previously rewarding begins to be associated with disadvantageous outcomes. In contrast, a number of studies suggested that gradual/procedural learning system seems intact in people with schizophrenia (Schmand, Kop, Kuipers, & Bosveld, 1992), (Exner, Boucsein, Degner, & Irle, 2006) but antipsychotic medication dosage, particularly those with high levels of dopamine 2 (D2) receptors blockades, may exert a negative effect on this system.

Social environments are dynamic with constant rapid changes, hence social situations require a rapid behavioural adjustment in response to ever-changing social feedback. People with schizophrenia have impaired social functioning and recent studies have shown that they also have impaired social reward processing (Catalano, Heerey, & Gold, 2018; Robberegt & Fett, 2017). Social approval induces rewarding feelings and is associated with increased activation in regions and networks associated with reward (Izuma, Saito, & Sadato, 2008; L. Rademacher et al., 2010; Spreckelmeyer et al., 2009). In those with schizophrenia there is reduced activity in common reward brain regions during the experience of social reward (Lee & Reavis, 2017), suggesting that they may have a reduced experience of the rewarding feeling of positive social attention. Positive social interactions have benefits for mental well-being and give life a sense of meaning (Uchino, Cacioppo, & KiecoltGlaser, 1996). In particular receiving praise and attention from others improves self-esteem (Hill, 1987) and increases motivation (Leary, 2007). Although social reward has major impacts on functional outcome, only recent efforts have explored social reward processing in schizophrenia.

Further behavioural evidence suggests that the RL difficulties to be more pronounced in learning from positive rather than negative feedback (Gold et al., 2008). This provides a further link between the effects of impaired RL and negative symptoms as learning preferentially from negative outcomes is likely to lead to behavioural avoidance, social withdrawal and have a negative impact on motivation. This hypothesis is supported by recent research suggesting that the magnitude of RL impairment, particularly for positive feedback, is associated with negative symptoms severity (Gold et al., 2012).

Despite the significance of RL problems in people with schizophrenia there is no therapy targeting this problem. The impact that a course of CR has on RL problems in people with schizophrenia has recently been explored (Cella et al., 2014). The results of the study show that this therapy can improve the sensitivity to positive and negative feedback and that improvement in these parameters were moderated by negative symptoms severity. However, this study used a standard CR protocol and may not have achieved the maximum effect on RL problems. Further the pilot nature of this study did not allow investigating the retention of RL improvements and more crucially how these may impact cognitive and negative symptoms and more broadly recovery. Reward learning difficulties in people with schizophrenia are associated with negative symptoms (NS) and it is plausible that by reducing RL difficulties a reduction in NS could be observed.

It is proposed that the structure of CR enhances rewards and motivation to engage in increasingly challenging tasks and this is a potential mechanism by which CR can achieve functional outcomes in this group. The specific CR interventions used in this study will be a computer-based program, CIRCuiTS (Computerized Interactive Remediation of Cognitive and Thinking Skills). To enhance RL, the therapy where possible, will be delivered individually with 1 participant to one therapist.

### **Significance**

Maximising the effect of interventions such as CR requires an understanding of the mechanisms of improvement from this therapy. Currently CR is undertaken over around 3 months with 2 to 4 sessions per week. Understanding the mechanisms of effect may enable improvements in the programs that enable more efficient delivery of this effective intervention.

### **2. Aims/Objectives:**

To investigate reward processing in individuals with Schizophrenia before and after completing a course of CR, and to compare this group with a control group of individuals with Schizophrenia and a matched non-clinical group. In addition, to explore whether working memory and negative symptoms mediate change in reward processing after CR.

**Aim 1:** To investigate reward learning in individuals with schizophrenia before and after engaging in a course of CR consisting of at least 20 sessions.

Hypothesis 1A: Participants with schizophrenia will demonstrate deficits in learning in both the social and non-social conditions. These differences in learning will be linked to aberrant activity in the dopamine system at a neural level in the prefrontal cortex and subcortical structures such as the basal ganglia compared with healthy controls.

Hypothesis 1B: Participants that complete CR will demonstrate improved learning in both the social and non-social conditions, again reflecting improved neural activity within the prefrontal and basal ganglia regions.

**Aim 2:** To investigate whether social processing working memory is a mediator of changes in reward processing following the interventions.

Hypothesis 2A: Patients with schizophrenia will show an additional deficit in social reward learning, relative to non-social reward learning.

Hypothesis 2B: CR therapy will attenuate socially specific deficits in reward learning.

**Aim 3:** To investigate whether working memory is a mediator of changes in reward processing following the interventions

Hypothesis 3A: Working memory will mediate improved reward processing in patients following CR therapy.

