**Experimental Task:**

During functional MRI imaging, participants will complete a computerised experimental task. This is a simple reinforcement learning task with two conditions, a social reward condition and a non-

social reward condition (see figure 1 below). Participants view an image on a computer screen, a leaking bucket on the non-social condition, and a face in the social condition. The goal is to fill the bucket with water (non-social condition) or to make the person smile (social condition). Three button responses are available to achieve these goals, represented on the screen by a square (left button), diamond (middle button) and pentagon (right button). Participants are told that one of these will; probably be a good choice (fills bucket or increases smile), while other choices may be poor choices (opposite effect). They must try to learn which buttons are the best responses by trial and error. The reward probabilities of each choice evolve over time however, requiring participants to continually track choice outcomes, and switch buttons over time to achieve their goal. Participants are encouraged to make button presses as quickly as possible (about 2-4 presses per second). Buttons A, B and C are randomly assigned to each reward probability for each task block. There are 10 blocks in each condition (social and non-social conditions). Blocks range from 20 to 45 seconds in length, allowing for hundreds of button choices per block, and thousands per condition. Completing both task conditions takes approximately 12 minutes. The task was developed by [name] for this study, and implemented in Matlab (Mathworks) using the Cogent 2000 toolbox (Wellcome Department of Imaging Neuroscience, Queen Square, London). During the fMRI experiment the task was seen by participants through a tilted mirror attached to the head coil on the MRI scanner. Responses were made on a commercially available MR-compatible response box(Current Design, <https://www.curdes.com/>).

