**Fig. 2**

Schematic diagram for the reward learning experimental task. Left Panel: Non-social reward condition, Right Panel: Social reward condition. Top: Four choices are illustrated in each condition, with progress towards the goal from left to right (filling the bucket or making the person smile). Middle: The reward probabilities are identical in the social and non-social learning conditions. At each point in time there is one optimal button choice, and reward probabilities of each choice change during each task block. Bottom: The actual choices of a test participant are illustrated, and the value of each button calculated, based on the feedback available to that participant. While the non-social choices are close to optimal, learning in the social condition is less efficient. Participants are familiarised with the task and perform two blocks of each condition prior to brain scanning.

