### **9.2 Statistical Analysis**

Participants' medication dosages will be converted to olanzapine equivalents using Leucht et al. (2016) guidelines. Outcome measures will be analysed using the SPSS Version 27 software package. A series of 3 (group: intervention, patient control; healthy control) x 2 (time: baseline, post-intervention) mixed factorial ANOVAs will be conducted to evaluate the treatment group differences for each of the outcome measures. If the normality assumption is violated, non-parametric analyses will be conducted.

Standard pre-processing of the functionally weighted images is carried out using SPM12 (<http://www.fil.ion.ucl.ac.uk/spm/software/spm8>, 2013; Friston, 2003). The pre-processing steps follows: slice timing on the functional images, to correct for differences in slice acquisition times within each volume using the middle slice as reference; realignment (estimate and reslice) on the functional images, to correct for inter-scan movement within each run (defined as >3 mm translation, >2 degrees rotation); co-registration of the functional and structural images; segmentation of the structural image, with heavy regularisation (0.1) recommended for MP2-RAGE sequence; normalization of the resliced images into a standardized, stereotaxic space (according to the Montreal Neurological Institute template); and smoothing of normalized images with a 8mm full-width-at-half-maximum isotropic Gaussian kernel.

We will adopt the General Linear Model approach for event-related designs will be conducted using SPM8 (<http://www.fil.ion.ucl.ac.uk>). For the first-level analysis task-related changes in blood-

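### Hypotheses 2A and 2B compare social with non-social learning, but the planned group-by-time ANOVA has no condition factor and no difference score, so it does not test them as written

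*Protocol*

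**What the plan says.** Protocol section 2 places two hypotheses under Aim 2. The first is "Hypothesis 2A: Patients with schizophrenia will show an additional deficit in social reward learning, relative to non-social reward learning". The second is that "CR therapy will attenuate socially specific deficits in reward learning". Aim 2 itself reads "To investigate whether social processing working memory is a mediator of changes in reward processing following the interventions".

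Section 9.2 specifies the behavioural analysis: "A series of 3 (group: intervention, patient control; healthy control) x 2 (time: baseline, post-intervention) mixed factorial ANOVAs will be conducted", with the purpose "to evaluate the treatment group differences for each of the outcome measures". The factors and their levels are listed, and condition is not among them.

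The later part of section 9.2 says that learning parameters will be estimated for each participant in each task condition. Second-level group analyses will then look at patients against controls and at what CR changed. No comparison of the two conditions is named there.

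The task description in section 4.2 says "There are 10 blocks in each condition (social and non-social conditions", and the legend to Fig. 2 says "The reward probabilities are identical in the social and non-social learning conditions".

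**The concern.** A claim that patients have an extra deficit in social learning is a claim about a difference between two differences. A model with group and time only, applied to each outcome in turn, answers a different question: whether groups differ, or change differently, on that one outcome. If social and non-social learning are entered as separate outcomes, the analysis yields two sets of p-values and no test of the gap between them. The easy next step is to read one significant and one non-significant result as evidence of social specificity, which it is not.

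Aim 2 adds to the difficulty. It is worded as a mediation question, yet neither of its hypotheses contains a mediator. The aim gives no help in working out which contrast was meant.

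**Working it through.** The protocol gives no power or effect size for learning, so there is no figure to reproduce. The check has a structural part and an illustration of size.

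**Structure.** Let S and N be a participant's social and non-social learning scores, and D = S − N.

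| Hypothesis | Term needed | Same test on D | In the section 9.2 ANOVA? |
|---|---|---|---|
| 2A | group × condition | patients v healthy controls on D at baseline | No |
| 2B | group × time × condition | CR v treatment as usual (TAU) on change in D | No |

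For two groups the two routes to 2B are identical. In a generated data set, the group × time F on D and the squared t for the three-way contrast were both 2.1416. A 3 × 2 ANOVA would therefore serve if D were an outcome, but the protocol does not define D.

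**Inputs for the illustration.**
- Group sizes: 40 patients and 20 healthy controls (section 3.3); 20 CR (section 3.1) and 20 TAU (section 3.2.1).
- Assumed: SD 1 in each condition, two-sided 5% level, between-condition correlation ρ of 0.3–0.6, and the same true effect d of 0.5–0.8 in both conditions, so that the socially specific claim is false. For 2B, d is in SD units of the change score.
- The only effect sizes in the protocol are 0.45 and 0.59 (section 1). They concern global cognition, not reward learning.

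**Method.** 20,000 simulated studies per setting, with a t-test for each condition and a t-test on D. The quantity of interest is

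P(social only) = P(S significant) − P(both significant).

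As a rough guide, with power π in each condition and independent scores this is π(1 − π). At d = 0.59 and 40 v 20, π ≈ 0.56, giving 0.56 × 0.44 ≈ 0.25. Positive correlation lowers it; the simulated value at ρ = 0.3 is 0.196.

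**Results with equal true effects: share of studies with social significant and non-social not.**

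| d | 2A (40 v 20), ρ = 0.3 | 2A, ρ = 0.6 | 2B (20 v 20), ρ = 0.3 | 2B, ρ = 0.6 |
|---|---|---|---|---|
| 0.5 | 20.1% | 14.6% | 18.6% | 13.7% |
| 0.6 | 19.1% | 14.8% | 20.1% | 15.0% |
| 0.7 | 17.2% | 12.9% | 19.7% | 14.9% |
| 0.8 | 12.5% | 9.3% | 16.9% | 13.3% |

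In the same runs the test on D rejects about 5% of the time two-sided, and about 2.5% in the predicted direction.

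**Power of the correct test.** The SD of D is √(2(1 − ρ)), and the standard error of the group difference is SD × √(1/n₁ + 1/n₂). Take a real specific effect, d = 0.8 social and 0.4 non-social, so a difference of 0.4.
- 2A, ρ = 0.3: SD 1.183, standard error 0.324, ratio 1.23, power 23%. At ρ = 0.7 power is 46%.
- 2B, ρ = 0.3: standard error 0.374, ratio 1.07, power 18%. At ρ = 0.7 power is 36%.
- At ρ = 0.3 the 95% interval half-widths are 2.002 × 0.324 = 0.65 for 2A and 2.024 × 0.374 = 0.76 for 2B.

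**The case against.** Three stronger readings are tempting, and the protocol does not support them.

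- *A reader might infer that 2A will be decided by one significant and one non-significant ANOVA.* No section says so, and none says outright that each condition gets its own ANOVA. That follows only from a per-outcome model without a condition factor. The error is one the plan invites, not a rule it states.
- *A reader might infer that the hypotheses cannot be tested at all.* They can. The task collects both conditions, the learning parameters are estimated by condition, and a 3 × 2 ANOVA on a difference score would do the job. The second-level wording in section 9.2 is also general enough to hold a condition contrast. What is missing is the named contrast or score.
- *A reader might count every discordant pair of results as a false social finding.* Discordance in either direction runs at about 19–40% for 2A over these settings. About half of that is non-social significant and social not, which would not support 2A.

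It can also be said that this is a mechanism pilot (section 9.1) and that mapping hypotheses to model terms often belongs in a statistical analysis plan. Pilot status does excuse low power. It does not cover a model whose factors the protocol itself lists and which omits the hypothesised term. An analysis plan that supplied the term would have to extend the stated design or define a new outcome.

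**Conclusion.** The point stands in this form: the one behavioural model that the protocol fixes lacks the terms that Hypotheses 2A and 2B need, and nothing else in the document names them. If the gap were filled by comparing significance across conditions, a spurious social-specific result in the predicted direction would arise in about 9–20% of studies for 2A and 13–20% for 2B, against about 2.5% for the interaction test. These rates rest on the assumed effect sizes, correlation, equal SDs and 5% level, and on simple two-group tests standing in for the three-group ANOVA. The structural conclusion depends on none of them. The mismatch between Aim 2 and its hypotheses is a separate drafting fault in the same section.

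**What to change.** 1. In section 9.2, add condition (social, non-social) as a within-subject factor for the learning outcomes, or define the social-minus-non-social learning score as an outcome.
2. Name the tests: for 2A, patients v healthy controls on that score at baseline; for 2B, CR v TAU on its change.
3. State the same condition contrast in the second-level fMRI models.
4. Report both as estimates with confidence intervals. At this sample size the tests will often be inconclusive even if the effect is real.
5. Reword Aim 2 so that it asks about socially specific reward learning, which is what 2A and 2B address.

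The cost is wording and a little more analysis. No extra visits, scans or participants are needed, since the task already has both conditions. The price in results is wide intervals. The change should be made before the data are analysed, so that the contrast does not look chosen afterwards.

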### **3. Study Design**

The study will be a pre post pilot study to investigate whether reward processing pathways are involved in the mechanism of action of cognitive remediation (CIRCuiTS). Matched control groups will be (1) people with schizophrenia receiving treatment as usual and (2) healthy controls without a Schizophrenia Spectrum Disorder.

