### **3.2 Study Population**

#### **3.2.1 Intervention and treatment as usual patient groups**

Participants (n=40) with a diagnosis of a schizophrenia spectrum disorder, based on current medical records will be recruited from the teams of the Metro South Addiction and Mental Health service (MSAMHS). Participants (n=20) that are not interested in completing CR will form the patient TAU control group and will complete the pre and post measures only. Thus, group intervention allocation selection will be based on individuals' preference to participate in CR. If a participant initially signs up to the intervention group but due to change in circumstances is unable to complete CR, they will be offered the opportunity to become part of the TAU group. Individuals that initially choose to complete CR therapy but then fail to complete more than 5 sessions will be re-allocated to the control (treatment as usual) group.

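### Aims 2 and 3, Hypothesis 3A and the general objective make mediation claims that a preference-allocated comparison at two time points cannot identify

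*Protocol*

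**What the plan says.** Section 2 (Aims/Objectives) uses mediation language in four places:

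- The general objective is "to explore whether working memory and negative symptoms mediate change in reward processing after CR". No aim or hypothesis takes up negative symptoms.
- Aim 2 asks whether a social-processing form of working memory is a mediator of change in reward processing. Its two hypotheses concern social versus non-social learning and do not mention mediation.
- Aim 3 asks the same of working memory.
- Hypothesis 3A states the expected result: "Working memory will mediate improved reward processing in patients following CR therapy".

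On the design, section 3 says: "The study will be a pre post pilot study to investigate whether reward processing pathways are involved in the mechanism of action of cognitive remediation". Section 3.2.1 says: "Thus, group intervention allocation selection will be based on individuals' preference to participate in CR". Those who choose CR but "fail to complete more than 5 sessions will be re-allocated to the control (treatment as usual) group". TAU patients "will complete the pre and post measures only". Section 9.2 has two analysed times, baseline and post-intervention, and states that "mixed factorial ANOVAs will be conducted to evaluate the treatment group differences for each of the outcome measures".

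**The concern.** A claim that working memory mediates the effect of CR on reward learning says three things: CR changes working memory, that change then alters reward learning, and nothing else explains the link. The first and third need CR and TAU patients to be comparable, and the mediator and outcome to share no unmeasured cause. The second needs the mediator to be seen to move before the outcome. Here the groups form by preference, membership can change after baseline according to sessions completed, and mediator and outcome change over the same interval.

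The direction is in real dispute within the protocol. Section 1 proposes reward learning as the route to improved cognition and motivational negative symptoms, and suggests that easing reward-learning difficulties could reduce negative symptoms. Section 2 puts working memory and negative symptoms upstream of reward processing. A positive test would be read as supporting the section 2 order even if the section 1 order were true. The Significance section hopes that knowledge of mechanism will improve CR programs, so the direction matters.

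**Working it through.** The protocol gives no power or mediation figure to reproduce, so the check asks how a conventional mediation test behaves in this design.

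**Inputs from the protocol.** 20 CR and 20 TAU patients (sections 3.1 and 3.2.1); two analysed times (section 9.2); effect sizes for CR of 0.45, and 0.59 when combined with rehabilitation (section 1). These effect sizes are for global cognition, not working memory or reward learning.

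**Assumptions.** Two-sided 0.05; link strength r between the two change scores of 0.3, 0.5 or 0.7; larger effects of 0.8 and 1.2 SD as a sensitivity range.

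**Test.** Let G be group, M the change in working memory and Y the change in reward learning. Fit M on G (path a), and Y on G and M (path b). Declare mediation if both paths are significant.

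**Models**, with d the CR effect and e1, e2 independent standard normal:

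- True mediation: M = dG + e1; Y = rM + √(1−r²)·e2. Path a is d and path b is r.
- Reversed: Y = dG + e1; M = rY + √(1−r²)·e2. Path a is r × d and path b is r.

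Both paths are non-zero under the reversed model too. For example, with d = 0.59 and r = 0.7, path a is 0.7 × 0.59 = 0.41 SD. The test must therefore fire more often as n grows, although working memory drives nothing.

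**Results at 20 v 20** (percentage of trials declaring mediation by working memory; r = 0.3 / 0.5 / 0.7; repeated runs differ by a point or two):

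| CR effect (SD) | True mediation | Direction reversed |
|---|---|---|
| 0.45 | 13 / 26 / 28 | 3 / 10 / 17 |
| 0.59 | 20 / 40 / 44 | 4 / 14 / 25 |
| 0.8 (assumed) | 32 / 63 / 69 | 5 / 21 / 41 |
| 1.2 (assumed) | not needed | 9 / 41 / 73 |

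The detection rates are low because path a alone has power of only about 30% at 0.45 and 46% at 0.59 with 20 per group, and the joint test cannot exceed that.

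**Other explanations, 20 v 20, effect 0.45.** If a common cause differs between the preference groups, mediation is declared in 6 / 15 / 21%. If CR acts on both measures in parallel with correlated residuals, it is declared in 12 / 26 / 28%, essentially the same as under true mediation.

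**Larger sample, 200 v 200, effect 0.45.** False mediation rises to 28 / 62 / 89% (reversed), 69 / 89 / 97% (common cause) and about 99% (parallel). The problem is identification, not pilot size.

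**A third visit.** The risk table in section 7.7 mentions a clinical assessment three months after treatment. It falls after the post-treatment reward measure, so it cannot place the mediator before that outcome.

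**The case against.** The strongest reply is that the protocol already frames this modestly. The objective says it explores, section 3 says pilot, and section 9.1 speaks of a possible mechanism and disclaims effectiveness. A hypothesis is not a conclusion, and no section commits the authors to reporting CR's mechanism on this result. That stands and lowers the severity. It does not remove the mismatch between exploring in the objective and an unqualified causal prediction in Hypothesis 3A.

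Four stronger readings are tempting but not supported:

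- A reader might infer that the ANOVAs are meant as the mediation test and fail at it. They carry no information on mediation: permuting outcome changes within group left the group-by-time F at 1.60 while the mediator slope fell from 0.59 to 0.02. But section 9.2 gives them only the purpose of comparing groups. A mediation model may sit in an analysis plan that is not shown, so its absence is no finding.
- A reader might take the highest reverse-direction rates, above 70%, as the expected size. Those need effects near 1.2 SD, which appear nowhere in the protocol.
- A reader might infer that patients are measured at two visits only. The wording in section 3.2.1 concerns TAU patients and may simply contrast with attending CR, section 7.7 mentions a third assessment, and the schedule figure is not shown. What is supported is that two times are analysed.
- A reader might say that an analysis plan can repair this. It can add a model, but not randomisation or an earlier mediator measurement.

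**Conclusion.** The point holds in limited form. The mediation wording of Aims 2 and 3, Hypothesis 3A and the general objective goes beyond what a non-randomised comparison at two analysed times can identify, and section 1 offers the reverse order as a serious rival. The study can show whether changes in working memory and reward learning go together among patients; it cannot show which drives which.

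At the protocol's effect sizes for global cognition and assumed links of 0.3 to 0.7, a reversed direction passes as mediation in about 3 to 25% of trials, and true mediation is found in about 13 to 45%. At assumed effects of 0.8 to 1.2 SD the reverse-direction rate is about 5 to 73%. These sizes rest on the assumed links, on transferring global-cognition effects to other measures, and on the joint-significance test. The identification problem does not depend on them. Severity is minor to moderate: it should be changed, but it does not invalidate the pilot.

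**What to change.** 1. Reword Aims 2 and 3, Hypothesis 3A and the negative-symptom clause of the objective as exploratory associations, for example: change in working memory is associated with change in reward learning among patients.
2. Name in advance one working-memory score from the cognitive battery already collected. The protocol does not say which component serves this purpose.
3. In patients, regress change in the learning parameter on change in that score, with the group originally chosen and both baselines as covariates. Report the coefficient with a 95% CI. Using the original choice keeps the session-count re-allocation out of the group variable; it does not remove confounding by preference.
4. Show the reversed model beside it, and state that no conclusion about mediation or direction will be drawn.
5. Reconcile the three-month assessment in section 7.7 with the two times in section 9.2.

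The cost is an amendment to wording and two regressions on data already planned, with no new visits. The downside is a weaker claim. Any claim about temporal order would need working memory measured during treatment, before the outcome, and self-selection into CR would still limit a causal reading.
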